6.1.2 MRI-based endpoints

15 March 2022, page 86/216

Table 7 MRI-based endpoints

Endpoints	Combined Analysis Period	Extension Analysis Period
 PCBV at all assessments 	Y	Y
• CUAL, defined as new Gd+ T1 lesions plus new or enlarging T2 lesions without double-counting the lesions) at all assessments	Y	Y
• Number of Gd+ T1 lesions at all assessments	Y	Y
• Cumulative number of new or enlarging T2 lesions (relative to baseline) at all assessments	Y	Y
• Volume of MRI lesions (T2 lesions, T1 hypointense lesions) at all assessments	Y	Y
• Absence of MRI lesions (Gd+ T1 lesions, new or enlarging T2 lesions) at all assessments	Y	Y
 Proportion of Gd+ lesions at baseline evolving to PBHs at all assessments 	Y	Y

CUAL = cumulative number of combined unique active lesions; MRI = magnetic resonance imaging PBH = persistent black holes; PCBV = percent change from baseline in brain volume.

6.1.3 Other endpoints

Table 8 Other endpoints

Endpoints	Combined Analysis Period	Extension Analysis Period
Change from baseline in MSFC Z-score at all assessments	Y	Y
 Change in the SDMT score at all assessments 	Y	Y
• Change from baseline in SF-36v2 TM Health Survey domain and component scores	Y	Y

MSFC = Multiple Sclerosis Functional Composite; SDMT = Symbol Digit Modalities Test.

6.2 Safety endpoints

In order to investigate the long-term safety of ponesimod and the changes in safety in teriflunomide subjects switching to ponesimod 20 mg, analysis will be performed on all data in the core and extension studies combined, using the core baseline as a reference. In addition, safety data

15 March 2022, page 87/216

reference.

EudraCT 2016-004719-10 EDMS-ERI-207656619

Confidential

collected in the extension study will be analyzed independently, using the extension baseline as a

Table 9 details which endpoints will be analyzed for the Extension Analysis Period, and which for the Combined Analysis Period.

Table 9 Analysis of safety endpoints

Endpoints	Combined Analysis Period	Extension Analysis Period
Adverse events		
 Treatment-emergent AEs, SAEs, and AEs of special interest[#] AEs leading to premature discontinuation of study treatment 	Y* Y	Y Y
Cardiac safety		
• Treatment-emergent morphological ECG abnormalities (as defined by the ECG provider)	Y*	Y
 Absolute values by visit for 12-lead ECG parameters (HR, PR, QRS, QT, QTcB, QTcF) 	Y	Y
 Change from baseline values by visit for ECG parameters (HR, PR, QRS, QT, QT QTcB, QTcF) 	Y	Y
 Change in ECG parameters (HR, PR, QRS, QT, QT QTcB, QTcF) from pre-dose to selected post-dose assessments (1 h, 2 h, 3 h, 4 h) on Day 1 and on day of re-initiation of study treatment 	N	Y
Pulmonary safety		
• Absolute values and percent change from baseline in FEV ₁ and FVC at all assessments	Y	Y
• Treatment-emergent decrease from baseline $>20\%$ and $>30\%$ in FEV ₁ or FVC	Y	Y
• Treatment-emergent decrease from baseline >20 percentage points in % of predicted FEV ₁ and FVC	Y	Y
• Among subjects with a decrease of ≥ 200 mL or $\geq 12\%$ in FEV ₁ or FVC from baseline to EOT, reversibility defined as a decrease of < 200 mL or $< 12\%$ in FEV ₁ or FVC from baseline to EOS**	Y	N

15 March 2022, page 88/216

EudraCT 2016-004719-10 EDMS-ERI-207656619

Confidential

Table 9

Analysis of safety endpoints

Endpoints	Combined Analysis Period	Extension Analysis Period
 Absolute change from baseline to EOS versus change from baseline to EOT in FEV₁ and FVC (absolute and % of predicted)** 	Y	N
• Change in lung diffusion capacity as assessed by DL _{CO} (at selected sites only) expressed in absolute change (mL) and % of predicted value from baseline at all assessments	Y	Y
• Change from baseline to EOS versus change from baseline to EOT in DL _{CO} (absolute and % of predicted) (at selected sites only)**	Y	N
Other endpoints		
 Absolute values and change from baseline for HR, SBP, DBP and body weight at all assessments 	Y	Y
• Treatment-emergent notable blood pressure abnormalities##	Y	Y
 Absolute values and change from baseline for laboratory tests (hematology, blood chemistry, urinalysis) at all assessments 	Y	Y
• Treatment-emergent notable laboratory abnormalities##	Y	Y
 Change from baseline to EOS versus change from baseline to EOT in lymphocyte counts (absolute and percent change)** 	Y	N
• Treatment-emergent eC-SSRS suicidal ideation score of 4 or above, or a "yes" response on the eC-SSRS suicidal behavior item	Y	N

Cumulative safety data, i.e., AEs for the combined analysis period will only be presented for subjects who received 20 mg ponesimod in the core study.

The selection of AEs of special interest [see Appendix 4] is based on the anticipated risks of treatment with ponesimod; the final list of AEs of special interest will be defined in the SAP.

The selection of notable abnormalities considered for the analyses is based on standard definitions and the anticipated risks of treatment with ponesimod; the final list of abnormalities will be defined in the SAP.

^{**} Only for subjects who have no exposure to commercially available ponesimod prior to the EOS visit.

AE = adverse event; DBP = diastolic blood pressure; DL_{CO} = diffusing capacity for the lungs measured using carbon monoxide; eC-SSRS = electronic self-rated version of the Columbia-Suicide Severity Rating Scale; ECG = electrocardiogram; EOS = End-of-Study; EOT = End-of-Treatment; FEV_1 = forced expiratory volume in 1 second; FVC = forced vital capacity; HR = heart rate; QTcB = QT corrected for heart rate on the basis of Bazett's formula; QTcF = QT corrected for heart rate on the basis of Fridericia's formula; SAE = serious adverse event; SAP = statistical analysis plan; SBP = systolic blood pressure.

15 March 2022, page 89/216

Confidential

EudraCT 2016-004719-10 EDMS-ERI-207656619

The treatment-emergent period is defined as the time from first ponesimod administration in the applicable Analysis Period up to 15 days (inclusive) after last study treatment administration. This definition applies regardless of whether the subject receives commercially available ponesimod after completing study treatment.

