1.3.2.2 Pharmacodynamics in humans

Oral administration of ponesimod dose-dependently reduces the circulating lymphocyte count in humans. The maximum reduction from baseline of approximately 65–80% is achieved after a single dose of ≥50 mg, or 40 mg o.d. at steady state. The nadir in lymphocyte count is attained within 6–10 hours following a given single dose. There is no evidence of tachyphylaxis on lymphocyte count. Peripheral blood counts of both T and B cells are reduced by ponesimod, while NK cells and neutrophils are not reduced. Food, race and gender do not appear to relevantly affect the PD of ponesimod. Upon discontinuation of ponesimod, the lymphocyte count generally returns to within the normal range within 1 week.

15 March 2022, page 45/216

Confidential

EudraCT 2016-004719-10 EDMS-ERI-207656619

The magnitude of lymphocyte-count reductions seen with ponesimod in MS subjects was consistent with observations made after short-term treatment in healthy subjects. In the Phase 2 dose-finding study AC-058B201, at Week 24, the mean reductions from baseline in lymphocyte count were 49.8%, 65.3% and 68.6% in the ponesimod 10 mg, 20 mg, and 40 mg groups, respectively, compared to a mean increase of 3.3% in the placebo group. Lymphocyte counts remained stable on treatment and returned to baseline levels within 1 week following ponesimod treatment discontinuation.

More detailed information can be found in the IB [Ponesimod IB].

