3.2.3.1 End-of-treatment

The EOT visit will take place at Week 240 or at the time ponesimod is commercially available for treatment of MS in the subject's country (whichever occurs first). The EOT visit should preferably take place 1 day after the last dose of study treatment but no later than 14 days after the last dose of study treatment. The EOT may take place in case:

- of premature discontinuation of study treatment for subjects meeting the study specific criteria for permanent discontinuation of study treatment described in Section 5.1.12;
- the sponsor decides to stop the extension study;
- the subject or the investigator decides to discontinue the study treatment;
- ponesimod is commercially available for the treatment of MS in the subject's country.

In some countries, additional reimbursement negotiations and central formulary approvals will be needed before ponesimod becomes available. In this case, patients participating in the AC-058B303 study can continue to receive ponesimod until ponesimod is available in their local country, or for a maximum of 240 weeks. Patients will get access to the study drug for a maximum of 240 weeks. If ponesimod becomes available locally before the end of the 240 weeks in the AC-058B303 extension study, then patients will be considered as having completed the extension study and will be switched to commercially available supply if they wish to continue ponesimod treatment. For these patients, the switch to commercially available ponesimod should occur at the EOT visit, and commercially available ponesimod may be initiated on the day following last intake of study treatment.

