11.4.8.3.3 Reversibility of treatment-emergent decreases in FEV₁ and FVC

For the subset of subjects with a decrease of ≥200 mL or ≥12% in FEV1 or FVC from core baseline at EOT, the number and percentage of subjects with a decrease of <200 mL and <12% from core baseline to EOS** in FEV1 or FVC will be summarized for subjects who received ponesimod 20 mg in the core study only for the Combined Analysis Period using the SAF.

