11.4.8.5 Laboratory endpoints

Descriptive summary statistics by visit will be provided for observed treatment-emergent values and absolute change from core baseline for laboratory tests (hematology, blood chemistry, urinalysis) by core study treatment for the Combined Analysis Period using the SAF. These parameters will also be summarized descriptively for the Extension Analysis Period by core study treatment and overall using the EXTS.

Treatment-emergent laboratory notable abnormalities will be summarized for subjects who received ponesimod 20 mg in the core study only for the Combined Analysis Period using the SAF.

The definition for notable abnormalities is provided in Appendix 5 and include:

- Treatment-emergent laboratory test abnormalities based on normal ranges of the central laboratory, project-specific ranges, and common terminology criteria for adverse events (CTCAE) [CTCAE 2010; see Appendix 5]
- Treatment-emergent laboratory test abnormalities based on FDA guidance for DILI [FDA 2009b] (for ALT / AST / total bilirubin).

Lymphocyte count reversibility after EOT will be summarized descriptively by comparing the mean (and 95% CIs) for absolute change in lymphocyte counts from core baseline to EOS, and from core baseline to EOT.** This analysis will be performed for the Combined Analysis Period by core study treatment using the SAF.

** applies only to subjects who have no exposure to commercially available ponesimod prior to the EOS visit.

11.4.8.6 eC-SSRS

The number and percentage of subjects with a treatment-emergent eC-SSRS suicidal ideation score of 4 or above, or a "yes" response on the eC-SSRS suicidal behavior item will be summarized descriptively by core study treatment for the Combined Analysis Period.

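### Table 9 defines lung-function reversibility with *or* where Section 11.4.8.3.3 uses *and*, so some unrecovered falls would count as reversed

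*Protocol*

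**What the plan says.** Table 9 (Section 6.2, pulmonary safety) lists a reversibility endpoint for the Combined Analysis Period. Its population begins "Among subjects with a decrease of" at least 200 mL or at least 12% in FEV1 or FVC from baseline to EOT. The outcome is "reversibility defined as a decrease of" less than 200 mL *or* less than 12%, in FEV1 or FVC, from baseline to EOS.

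Section 11.4.8.3.3 describes the analysis of the same endpoint. The population is the same: "For the subset of subjects with a decrease of ≥200 mL or ≥12% in FEV1 or FVC from core baseline at EOT". The outcome is not: "the number and percentage of subjects with a decrease of <200 mL and <12"%, that is, both conditions together.

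Both places restrict the analysis to subjects with no commercial ponesimod before EOS. Neither says that reversal must be shown on the parameter that qualified the subject.

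On timing, Section 3.2.3.1 prefers EOT 1 day after the last dose and allows it "no later than 14 days after the last dose of study treatment". EOS is 30–44 days after permanent discontinuation (Section 3.2.4). EOT-to-EOS contrasts are also planned for mean FEV1 and FVC, for DLCO (Table 9), and for lymphocytes: "Lymphocyte count reversibility after EOT will be summarized descriptively by comparing the mean (and 95% CIs") for the changes to EOS and to EOT.

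**The concern.** A reversibility rule should ask whether a subject who met the entry condition no longer meets it. The entry condition is joined by *or*, so its negation must be joined by *and*. Table 9 joins the negation by *or*, and the entry and reversal conditions then overlap. A subject in the overlap is counted as recovered without any change in lung function.

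Reversibility is a listed safety endpoint, and bronchoconstriction is among the adverse events of special interest (Appendix 4). The error makes persistent loss look transient. Section 11.3.3 refers back to Section 6.2 for the safety endpoint definitions, so Table 9 cannot be dismissed as a loose summary of Section 11.

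A smaller, separate matter is that EOT stands in for the on-drug value. An EOT visit well after the last dose compares two off-drug values.

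**Working it through.** The protocol states no figure for this endpoint, so there is nothing to reproduce. The rules can be checked directly.

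**1. The overlap.** Let *b* be the baseline and *d* the fall, both in mL.
- Entry (both places): *d* ≥ 200 or *d/b* ≥ 0.12.
- Reversal, Table 9: *d* < 200 or *d/b* < 0.12.
- Reversal, 11.4.8.3.3: *d* < 200 and *d/b* < 0.12.

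For a single parameter, the rule in 11.4.8.3.3 is the exact negation of entry. The Table 9 rule overlaps with entry whenever exactly one threshold is met. The thresholds coincide only at *b* = 200/0.12 = 1,667 mL. Elsewhere the overlap lies between 200 mL and 0.12*b*:

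| Baseline | Fall that qualifies and also counts as reversed |
|---|---|
| 1.5 L | 180 to <200 mL |
| 3.0 L | 200 to <360 mL |
| 4.0 L | 200 to <480 mL |

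**2. Worked cases.**
- 3.2 L baseline, 300 mL fall (300/3,200 = 9.4%) at both EOT and EOS: reversed under Table 9, not under 11.4.8.3.3.
- 3.0 L baseline, fall growing from 250 mL (8.3%) at EOT to 350 mL (11.7%) at EOS: still reversed under Table 9.
- 3.0 L baseline, unchanged 400 mL fall (13.3%): not reversed under either rule.

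**3. Possible size.** The protocol gives no FEV1 distribution, so these inputs are assumptions; falls are normal, with 400,000 draws per scenario.
- Set A: baseline mean 2.8–3.6 L, SD 0.6 L; mean fall 100–250 mL, SD 200–300 mL.
- Set B: baseline mean 3.0–3.3 L, SD 0.6–0.7 L; mean fall 150–350 mL, SD 200–300 mL.

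With zero recovery (EOS fall equal to EOT fall), Table 9 labels about 31–81% of qualifying subjects reversed in set A and about 30–68% in set B, against 0% under *and*. If every subject recovers the same fraction of the fall, the excess labelled reversed by Table 9 is about 20–50 percentage points at 50% recovery. At 75% recovery it is at most about 6 points in set A and 9 in set B.

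**4. Parameter matching.** Take an unchanged 400 mL FEV1 fall from 3.0 L, with a 50 mL FVC fall from 4.0 L. Entry is met on FEV1. If FEV1 or FVC is read as either one, reversal is met on FVC, even with *and* between the thresholds.

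**5. EOT timing.** Section 1.3.2.1 gives a half-life of about 32 h. Fraction remaining = 0.5^(hours/32):
- 1 day: 0.5^0.75 = 59%
- 7 days: 0.5^5.25 = 2.6%
- 14 days: 0.5^10.5 = 0.07%

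The protocol also says "Upon discontinuation of ponesimod, the lymphocyte count generally returns to within the normal range within 1 week" (Section 1.3.2.2), and that pulmonary function returned to baseline off drug, without a time course (Section 1.3.2.4). A day-14 EOT lies inside the 15-day treatment-emergent window of Section 11.4.8, so that window does not remove it.

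**The case against.** The analysis section already has the right wording, so if the programmer follows 11.4.8.3.3 nothing is miscounted. The endpoint is descriptive, is not among the main safety endpoints in the synopsis, and does not drive subject management. Mean changes to EOT and to EOS are reported separately, so a group-level failure to recover would still be visible. All of this stands and limits the consequence. It does not remove a contradiction between two current sections, one of which gives a wrong answer.

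A reader might infer that Table 9 turns every unrecovered subject into a reversed one, or that 30–80% of the reported reversals will be false. Neither is supported. Only falls between the two thresholds are affected. The percentages assume no recovery in anyone, whereas Section 1.3.2.4 reports recovery after stopping.

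The wording FEV1 or FVC can fairly be read parameter by parameter. It is ambiguous rather than wrong.

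On timing, a reader might infer that EOT is unusable as the on-drug value and should be replaced by the last value taken on drug. The documents do not support that. One day after the last dose is preferred. EOT visits delayed by a long interruption (Section 8.3.10) should mostly drop out under the default 15-day limit (Sections 11.1.4.2 and 11.4.8). No share of late EOT visits can be derived. After Week 4, scheduled spirometry and DLCO are 48 weeks apart, so a substituted value could be nearly a year old. A 1-day cut-off would also discard EOT values at day 2 or 3, when 35% or 21% of drug remains.

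**Conclusion.** The contradiction is real, and Table 9 is wrong as written. Its rule is not the complement of the entry rule and can label an unchanged or worse fall as reversed. The error is confined to falls between 200 mL and 12% of baseline and runs in the reassuring direction. The zero-recovery range of roughly 30–80% rests on assumed distributions and is a worst case, not a forecast; the disagreement is small when recovery is nearly complete. No type I error or power is involved.

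The EOT timing point is secondary. For subjects with a late EOT, the contrasts in FEV1, FVC, DLCO and lymphocytes can be understated, and a subject who recovers before a late EOT may never enter the reversibility subset. For lung function this is an inference from drug elimination, since no recovery time course is given.

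**What to change.** 1. In Table 9, change the reversal condition to a fall of <200 mL *and* <12%, matching Section 11.4.8.3.3. This costs one word.
2. In both places, state that reversal is judged on the same parameter (FEV1 or FVC) that met the entry rule, and how a subject who qualified on both is counted. This costs one sentence.
3. Keep EOT as the comparator. Add a sensitivity summary of the EOT-to-EOS contrasts (FEV1, FVC, DLCO, lymphocytes) by days from last dose to EOT. This needs one derived variable and one extra table, with no new data collection, and avoids substituting old on-drug values.

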1.2 Sphingosine-1-phosphate receptors

S1P plays a central role in lymphocyte trafficking [Cyster 2005, Brinkmann 2007, Brinkmann 2010, Schwab 2007, and references therein]. S1P is synthesized and secreted by many cell types, including platelets, erythrocytes, and mast cells, and elicits a variety of physiological responses [Cyster 2005, Alvarez 2007]. Among other effects, lymphocyte egress from primary and secondary lymphoid organs is dependent on the S1P1 receptor. S1P1 receptor modulators block lymphocyte migration out of lymphoid tissue into the lymphatic and vascular circulation, thereby reducing peripheral lymphocyte counts and preventing lymphocyte recruitment to sites of inflammation. Following withdrawal of an S1P1 receptor agonist, the functional lymphocytes return to the circulation from their sites of sequestration. Other functions that do not rely on homing mechanisms, such as antibody generation by B lymphocytes, first-line immunological protection by granulocytes and monocytes, and antigen-dependent T-cell activation and expansion, are not affected by this mechanism [Pinschewer 2000].

S1P itself induces pleiotropic effects, which are mediated by a family of five G protein-coupled receptors, S1P1–S1P5, located on endothelial cells, vascular and cardiac smooth muscle cells, and cardiac myocytes [Alvarez 2007, Brinkmann 2007, Brinkmann 2010]. The first S1P receptor modulator, fingolimod (FTY720, Gilenya®), which has been approved by the FDA and the EMA for the treatment of MS, is not selective for the S1P1 receptor but interacts with S1P3, S1P4, and S1P5 [Brinkmann 2007, Brinkmann 2010]. Two other S1P receptor modulators - siponimod and ozanimod (which bind to S1P1 and S1P5) have also been approved for MS in some countries.

Confidential

EudraCT 2016-004719-10 EDMS-ERI-207656619

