5.1.11 Premature discontinuation of study treatment

In the study, the premature discontinuation of study treatment is defined as a permanent discontinuation of study treatment earlier than the planned treatment duration of 240 weeks or ponesimod is commercially available. The decision to prematurely discontinue study treatment may be made by the subject, the investigator, or the sponsor.

A subject has the right to prematurely discontinue study treatment at any time by withdrawal from treatment only, or by withdrawal from treatment and any further participation in the study.

The investigator should discontinue study treatment for a given subject if, on balance, she/he believes that continued administration would be contrary to the best interests of the subject. In the event of clinically significant progression of the disease as judged by the investigator, the investigator should consider switching to another potentially more effective therapy, discuss alternative treatment options with the subject, and document the outcome of this discussion in the medical records.

15 March 2022, page 71/216

Confidential

EudraCT 2016-004719-10 EDMS-ERI-207656619

Premature discontinuation of study treatment may also result from a decision by the sponsor, e.g., in the event of premature termination or suspension of the study [see Section 9.3].

The main reason for discontinuation of study treatment, and whether the discontinuation of study treatment is the decision of the subject, the investigator, or the sponsor must be documented in the eCRF.

A subject who prematurely discontinues study treatment and withdraws consent to participate in any further study assessments is considered withdrawn from the study. Subjects who die or are lost to FU are also considered as withdrawn from the study. Withdrawal from the study and FU medical care of subjects withdrawn from the study is described in Sections 9.2 and 9.4, respectively.

In the event of premature discontinuation from study treatment due to any reason, the investigator should consider prescribing appropriate treatment for MS according to the local clinical practice and availability. The investigator should exercise caution when considering the switch to another immunomodulatory MS treatment.

5.1.12 Study-specific criteria for interruption / premature discontinuation of study treatment and management of clinically relevant events

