5.2 Concomitant therapy

A therapy that is concomitant to study-treatment is any treatment that is either ongoing at the start of study treatment or is initiated during the study treatment period, or up to 30 days after the end of study treatment. All study treatment concomitant therapies will be recorded on the Concomitant Medications page of the eCRF. In addition, all medication taken by the subject at EOS of the core study, i.e., all medication ongoing or started at this time, will be recorded on the Concomitant Medications page of the eCRF.

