All of the above measures are recommended for consideration on a temporary basis during the COVID-19 pandemic to enable continuity of treatment and to ensure that subject assessments, particularly those assessing relapse and safety, continue as outlined in the protocol without imposing health risk to subjects, their families, and site staff. Every effort should be made to complete all protocol-required assessments. Investigators should use their clinical judgment and benefit risk assessment in determining if a subject can continue study treatment in the absence of on-site clinic visits. If remote visits are not possible, or if in the investigator's judgment, appropriate safety monitoring is not feasible in a remote setting, the investigator should consider temporarily interrupting study treatment (for a maximum of 12 weeks per protocol) or discontinuing study treatment and initiating treatment with another available disease modifying treatment (DMT).

STUDY CONDUCT RELATED TO COVID-19 VACCINE DEPLOYMENT FOR NONCOVID-19 CLINICAL TRIALS

Current guidelines from global MS societies recommended that people with MS should be vaccinated against COVID-19. 1,2,3 Having MS does not increase the risk of COVID-19 virus infection or the risk to develop severe forms of the infection more than the general population and it is important that DMT in MS patients is continued and maintained. 4 It is therefore recommended that people with MS currently taking a DMT, including ponesimod, continue with their treatment unless advised to stop by their treating physicians (e.g., MS patients on DMT with risk factors for severe COVID-19 infections).

No clinical data are available on the efficacy and safety of vaccinations in patients taking ponesimod.

15 March 2022, page 214/216

EudraCT 2016-004719-10 EDMS-ERI-207656619

Confidential

Based on preclinical data, vaccinations may be less effective if administered during treatment.

There are 4 main types of COVID-19 vaccines (all non-live) that are currently available (see below). For a complete overview of the COVID-19 vaccine landscape, please refer to the WHO website.⁵

- **mRNA vaccines** are based on the SARS-CoV-2 spike glycoprotein antigen encoded by RNA and formulated in lipid nanoparticles;
- **Protein subunit vaccines** based on full-length spike protein (S), receptor-binding domain (RBD), non-RBD S protein fragments, and non-S structural proteins;

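### The reversibility summaries exclude only users of commercial ponesimod, so a subject who starts another lymphocyte-lowering drug before EOS is counted as an off-drug value

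*Protocol*

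**What the plan says.** Table 9 in Section 6.2 puts a double asterisk on four EOT-versus-EOS rows: reversibility of FEV1/FVC decreases, change in FEV1 and FVC, change in DLCO, and change in lymphocyte counts. The footnote reads "Only for subjects who have no exposure to commercially available ponesimod prior to the EOS visit".

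Section 11 repeats the restriction. In 11.4.8.3.1 it governs the plotted FEV1/FVC changes. In 11.4.8.3.3, among subjects with a decrease at EOT, it governs "the number and percentage of subjects with a decrease of <200 mL and <12% from core baseline to EOS". In 11.4.8.5, "Lymphocyte count reversibility after EOT will be summarized descriptively by comparing the mean (and 95% CIs") for change to EOS and to EOT, and the note says that this "applies only to subjects who have no exposure to commercially available ponesimod prior to the EOS visit".

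On treatment after stopping:

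- Section 5.1.11: after premature discontinuation for any reason, "the investigator should consider prescribing appropriate treatment for MS according to the local clinical practice and availability". It then urges caution about a switch to another immunomodulatory MS drug.
- Section 5.1.12.7.1: a subject with uveitis who needs a prohibited immunosuppressant must come off study treatment.
- Appendix 12, where remote visits or safe remote monitoring are not feasible: consider interrupting, or "discontinuing study treatment and initiating treatment with another available disease modifying treatment (DMT)". The regional-crisis guidance after it says the same.
- Section 5.2 counts as concomitant any therapy that is ongoing at the start of treatment "or is initiated during the study treatment period, or up to 30 days after the end of study treatment". Section 5.2.3 forbids other MS disease-modifying drugs and immunosuppressants as concomitant therapy.

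EOS is 30 to 44 days after permanent discontinuation (Sections 3.2.4 and 8.4.1).

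**The concern.** A reversibility comparison needs an EOS value taken off any drug that acts on the same measurement. The footnote accepts this principle, since it removes subjects who are back on ponesimod, but applies it to one product only.

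The restriction also changes who is left. Once subjects who switched to commercial supply are removed, the set consists of premature stoppers and Week 240 completers without commercial drug. The premature stoppers are the group for whom Section 5.1.11 asks that other MS treatment be considered.

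Lymphocytes are the clear case. Section 1.2 says that S1P1 receptor modulators keep lymphocytes in lymphoid tissue, "thereby reducing peripheral lymphocyte counts and preventing lymphocyte recruitment to sites of inflammation", and names approved drugs of the S1P modulator class. Section 5.2.3 describes rituximab and ocrelizumab as lymphocyte-depleting. A subject on such a drug at EOS would have a low count that says nothing about recovery from ponesimod, yet it would enter the mean as if it did.

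**Working it through.** The protocol gives no planned figure for these endpoints, so there is nothing to reproduce. The check has three steps.

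**1. Should an untreated subject have recovered by EOS?** Inputs: half-life about 32 h (Section 1.3.2.1); lymphocytes back to baseline within 1 week of stopping (Section 1.3.2.2). Half-life in days = 32/24 = 1.333. Fraction of drug remaining = 0.5^(days/1.333).

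- Day 7: 5.25 half-lives, about 2.6% remaining.
- Day 30: 22.5 half-lives, under 0.0001% remaining.

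So a low count at EOS in an untreated subject would properly suggest non-reversal. For the same reason, a low count caused by another drug would be mistaken for it.

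**2. Can another drug be present at EOS under the text?** Section 5.1.11 and Appendix 12 set no wait until EOS. Sections 5.2 and 5.2.3, read together and literally, forbid other disease-modifying drugs until 30 days after the end of treatment. That reading does not close the gap:

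- it sits in conflict with Section 5.1.11 and Appendix 12;
- EOS may be as late as day 44, which leaves 44 - 30 = 14 days uncovered;
- a subject who breaches it still meets the footnote and stays in the analysis.

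**3. How large could the effect be?** Let p be the share of the analysed set on a replacement drug at EOS and e that drug's mean lymphocyte reduction, with everyone else fully recovered. Mean percent change at EOS = -p × e. Neither p nor e is in the document. For e I show zero, 30% (assumed), and 65.3%, which is ponesimod's own mean reduction at 20 mg at Week 24 of the Phase 2 study (Section 1.3.2.2).

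| p | e = 0 | e = 30% | e = 65.3% |
|---|---|---|---|
| 5% | 0 | -1.5 | -3.3 |
| 10% | 0 | -3.0 | -6.5 |
| 20% | 0 | -6.0 | -13.1 |

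Entries are percentage points; full reversal gives 0. For example, 0.10 × 65.3 = 6.53. With e equal to 65.3%, apparent recovery of the EOT drop is 1 - p, so 90% at p = 10% where the truth is 100%.

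I give no such table for FEV1, FVC or DLCO, because the protocol reports no lung effect of any replacement drug.

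**The case against.** A reader might infer that the protocol steers stoppers to other S1P modulators. It does not. Section 5.1.11 says only that treatment should be considered, advises caution with another immunomodulator and names no class. Fingolimod, siponimod and ozanimod appear only in the background. Section 5.2.3 names the lymphocyte-depleting agents as forbidden, not as options. A reader might also infer that replacement therapy will generally look like failed reversal. That holds only for drugs that act on the measurement. For lung function the documents give no support.

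The sponsor could answer that the footnote matches the design: commercial ponesimod is the one drug expressly permitted straight after the last dose, and Section 5.2.3 forbids the others. This explains the wording, but fails as protection for the reasons in step 2 of the working. It does limit the exposure: on the strict reading, contamination needs a late EOS visit and a drug started within the preceding 14 days that has already taken effect.

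Two further points stand. The analyses are descriptive (Section 11), so no error rate is affected, and any bias runs against ponesimod. And plain exclusion is not neutral: subjects stopped for confirmed lymphopenia (Section 5.1.12.2) or lung-function decline (Section 5.1.12.3) may be the ones given another drug, and dropping them could flatter ponesimod.

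Section 11.3.3 leaves detail on safety variables to the SAP, which I have not seen. The restriction itself, however, is fixed in the protocol.

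**Conclusion.** The restriction is incomplete as written. It lets a subject on a lymphocyte-lowering replacement drug count as an off-drug EOS value, and the protocol's text allows that situation to arise. The consequence is clear in kind for lymphocytes; for FEV1, FVC and DLCO a broader rule is a matter of consistency only.

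The size cannot be established from the document. The shifts of -3.3 to -13.1 points assume shares of 5% to 20% and an effect equal to ponesimod's; weaker drugs give less, and drugs that leave lymphocytes alone give none. The point is worth correcting because the summary speaks directly to a safety property of the drug and the repair is cheap. It does not touch the main efficacy results.

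**What to change.** In Table 9 and Sections 11.4.8.3.1, 11.4.8.3.3 and 11.4.8.5, restrict the main reversibility summary to subjects with no commercially available ponesimod and no other MS disease-modifying or immunosuppressive drug between the last study dose and the EOS assessment. Summarise subjects who started such a drug separately, with their reason for stopping, and repeat the summary with them included, so that any loss of informative stoppers is visible.

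The cost is one footnote in four places, a somewhat smaller main set and one extra summary. No new data are needed: Section 7.3 already records all therapies, with start and stop dates, up to EOS.

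Separately, the sponsor should reconcile Sections 5.2 and 5.2.3 with Section 5.1.11 and Appendix 12 on other disease-modifying drugs before EOS. Which rule should govern is a clinical matter and is not proposed here.
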